# 9.7.1.8 Safety analysis

Safety is to be analysed using the safety analysis set. Summary statistics related to safety data (sample size, mean, standard deviation, median, minimum and maximum for continuous variables; sample size and ratio for categorical variables) are to be calculated by treatment group based on the actual treatment received. Safety endpoints include adverse events, laboratory values, vital signs, weight, physical examination, standard 12-lead ECG, neurological symptoms and blood CD4+ cell count. In safety analysis, Day 1 is the start date of IMP administration.

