4.4 Extent of investigational medicinal product exposure and compliance

Duration of IMP exposure is defined as date and time of last IMP administration – date and time of first double-blind IMP administration + 14 days, regardless of unplanned intermittent discontinuations. Duration will be presented in days.

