5.2 Safety Population

Safety analysis set is a set of subjects to whom the IMP has been administered, and who had 1 or more evaluable, post-IMP administration safety data points. Safety endpoints include adverse events, laboratory values, vital signs, weight, physical examination, standard 12-lead ECG, neurological symptoms and blood CD4⁺ cell count. Patients in the safety population will be analyzed according to the treatment actually received at remission-induction period.

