- 2) Rescue Period (Open label): comprises from week 12 to week 24 for non-responders. Subjects with a reduction in the CDAI of less than 70 compared to baseline after finishing evaluation in Week 12 of the remission-induction period are to move on to the rescue period. The rescue period is to last 12 weeks, with 10 mg/kg of E6011 administered in an unblinded manner on Week 12, Week 13, Week 14 and every two subsequent weeks until Week 22.
- 3) Extension Period (Open label): comprises from week 12 to week 52 for responders at week 12 and from week 24 to week 64 for non-responders at week 12. Subjects who

finished evaluation at Week 12 of the remission-induction period and had a CDAI response of 70 or more, and subjects who moved on to the rescue period and finished evaluation at Week 24 with a CDAI response of 70 or more are to move on to their respective extension period. The extension period is to last 40 weeks, with 10 mg/kg E6011 administered in an unblinded manner every four weeks up to Week 48(responders) or Week 60(non-responders).

- 4) Post-Observation Period: After the extension period of the clinical trial has been finished or discontinued, examinations are to be carried out 28 days after the completion or discontinuation of the extension period and 70 days after the last administration of the IMP.
- 5) Follow-up Period: PML onset is to be investigated over the phone, etc. every 6 months in the two-year follow-up period after the last IMP administration.

Four analysis periods are defined:

- 1) Remission-induction period: as defined above.
- 2) Rescue period: as defined above. This period will be used only for adverse events endpoints.
- 3) Entire administration period comprises the remission-induction period, the rescue period, the extension period and the post-observation period as defined above.
- 4) Follow-up period: as defined above.

Analyses of the remission-induction period will be performed after the remission-induction period is completed. Analyses of the entire administration period (remission-induction period, rescue period, extension period and post-observation period) will be performed after the post-observation period is completed. Analysis of the follow-up period will be performed after the follow-up period is completed.

In all TFLs that are displayed by treatment groups they will refer to the remission-induction treatments.

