6.9.1 Adverse Events

Treatment-emergent adverse events are adverse events that developed or worsened during the treatment-emergent adverse event period (from first date of IMP until last date of IMP +70 days).

The primary focus of adverse event reporting will be on treatment-emergent adverse events. Post-treatment PML events will be described in a separate table, as well as pre-treatment, treatment emergent and post-treatment deaths.

Adverse events will be considered only in the period in which it starts.

The following summaries will be generated for the safety population.

- a. Overview of adverse events during all study and by analysis period, summarizing number (%) of patients with any
 - Adverse event
 - Treatment-emergent adverse event
 - Serious treatment-emergent adverse event
 - Non-serious treatment-emergent adverse event
 - Treatment-emergent adverse event leading to death
 - Treatment-emergent adverse event leading to permanent treatment discontinuation
 - Treatment-emergent adverse event related to study drug
- b. All adverse events during all study by primary SOC and PT, showing number (n) and percentage (%) of patients with at least 1 adverse event sorted by the SOC internationally agreed order. The other level (PT) will be presented in alphabetical order
- c. All treatment-emergent adverse events by analysis period and by primary SOC and PT, showing number (n) and percentage (%) of patients with at least 1 treatment-emergent adverse event sorted by the SOC internationally agreed order. The other level (PT) will be presented in alphabetical order

- d. All treatment-emergent adverse events related to IMP by analysis period and by primary SOC and PT, showing the number (n) and percentage (%) of patients with at least 1 treatment-emergent adverse event, sorted by the internationally agreed SOC order. The other level (PT) will be presented in alphabetical order
- e. All treatment-emergent adverse events by analysis period and by maximal severity, presented by primary SOC and PT, showing the number (n) and percentage (%) of patients with at least 1 treatment-emergent adverse event by severity (i.e., mild, moderate, or severe), sorted by the sorting order defined above.
- f. All treatment-emergent serious adverse events by analysis period and by primary SOC and PT, showing the number (n) and percentage (%) of patients with at least 1 serious treatment-emergent adverse event, sorted by the internationally agreed SOC order.

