6.11 Modifications from the Statistical Section in the Protocol

There are no modifications from the statistical section in the protocol.

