10 GENERAL FORMAT OF TABLES, FIGURES AND SUBJECT DATA

Tables and listings will be produced in accordance with the principles outlined by the ICH E3 guideline. All summary tables will be presented by treatment group and race (all, Japanese and non-Japanese).

The design of the tables will be clear and concise so that comparative reading is easily possible.

All descriptive variables will be tabulated. Quantitative variables will be described showing their number of available and missing observations, mean and its CI (95% level), median, standard deviation, the range (minimum and maximum) and the first and third quartiles. Frequency and percentage will describe qualitative variables.

Missing values will be tabulated with their frequency but will not be included in the calculation of percentages. Analysis will be based on observed cases, i.e., no replacement of missing data is planned in general except otherwise planned in the appropriate statistical methodology section (section 11, section 12 or 14).

Pharmacokinetic data (E6011 serum concentrations) will be summarized by treatment group and race (All, Japanese and Non-Japanese) and evaluation time, including the number of sample results, minimum, medium, maximum, mean, standard deviation and coefficient of variation (CV). In addition, geometric means and geometric CV will be also shown.

Serum E6011 concentration vs time curves will be prepared. A serum concentration profile will be prepared for each subject and shown individually on a single plot per patient. A plot showing all serum profiles generated per treatment group will be prepared.

Summary serum E6011 concentration vs time profiles will also be prepared. A geometric mean serum profile will be shown by treatment group individually and grouped by treatment.

Pharmacodynamic data (serum total FKN concentrations, faecal calprotectin and serum CRP concentration measured values, change and % change from baseline) will be summarized by treatment group, evaluation time and race (all, Japanese and non-Japanese), including the number of sample results, minimum, medium, maximum, mean, standard deviation and coefficient of variation (CV). In addition, geometric means and geometric CV will be also shown.

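### Adverse events on open-label E6011 in placebo-randomised patients are tabulated under placebo, and no table counts events from the first E6011 dose

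*SAP*

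**What the plan says.** SAP 6.1 describes five study periods but only four analysis periods: remission-induction, rescue (adverse events only), entire administration, and follow-up. The extension is reported only inside the third: "Entire administration period comprises the remission-induction period, the rescue period, the extension period and the post-observation period as defined above".

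The columns are fixed in the same section: "In all TFLs that are displayed by treatment groups they will refer to the remission-induction treatments". SAP 5.2 applies this to safety: "Patients in the safety population will be analyzed according to the treatment actually received at remission-induction period".

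SAP 6.9.1 runs the treatment-emergent window from the first dose of study product to 70 days after the last, with no restart at the switch to open-label drug. Each event is assigned to the period in which it starts. Table c is typical: "All treatment-emergent adverse events by analysis period and by primary SOC and PT", counting patients with at least one event. Items a and b also cover the whole study.

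Protocol 9.1 gives open-label E6011 to all who continue after Week 12. Non-responders receive it in the rescue period and, if they then respond, in the extension. Week 12 responders go straight to the extension. A secondary objective (SAP 3.3.2) is the efficacy and safety of long-term E6011.

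**The concern.** After Week 12 nobody receives placebo, yet the placebo column continues. Take a placebo-randomised patient who responds at Week 12 and enters the extension. An event starting there, on E6011, appears only in the placebo column of tables that also hold that patient's events on placebo. For a placebo-randomised non-responder, rescue events are all on E6011 but stand under placebo in the rescue table. Any extension events again appear only in the pooled count.

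At stake is the long-term safety objective. By 1:1 allocation of the 25 patients enrolled (Protocol 9.7.2), about 12 or 13 were randomised to placebo. If most of them reach Week 12, roughly half of the E6011-exposed patients sit in the placebo column. An effect of E6011 can then look like background, and no planned table states how many exposed patients had a given event after starting the drug.

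**Working it through.** The plan gives no figure on this point to reproduce. Its only design figure, the probability of confirming efficacy, does not enter.

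**Inputs.** Open-label E6011 starts at Week 12. The last scheduled dose is Week 22 (rescue failure), Week 48 (Week 12 responder) or Week 60 (rescue then extension) (Protocol 9.4.1). The window ends 70 days, or 10 weeks, after the last dose (SAP 6.9.1).

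**Step 1: share of a placebo-column patient's window after the first E6011 dose.** Window end = last-dose week + 10; share = (window end − 12) / window end.

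| Path | Window end | Weeks after E6011 start | Share |
|---|---|---|---|
| Rescue failure | 22 + 10 = 32 | 20 | 20/32 = 62.5% |
| Week 12 responder, completes extension | 48 + 10 = 58 | 46 | 46/58 = 79.3% |
| Rescue then extension, completes | 60 + 10 = 70 | 58 | 58/70 = 82.9% |

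**Step 2: how far the two columns converge.** The documents give no event risk, so this is an illustration. Assume an event that never occurs on placebo and has a constant risk r per 12 weeks from the first E6011 dose to the end of the window. For window end T, the placebo column shows 1 − (1 − r)^((T − 12)/12) and the E6011 column shows 1 − (1 − r)^(T/12).

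| Path | r = 5%: placebo vs E6011 column | r = 10%: placebo vs E6011 column |
|---|---|---|
| Rescue failure | 8.2% vs 12.8% | 16.1% vs 24.5% |
| Week 12 responder | 17.9% vs 22.0% | 33.2% vs 39.9% |
| Rescue then extension | 22.0% vs 25.9% | 39.9% vs 45.9% |

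The true placebo figure is 0% in every row. At r = 5% the ratio of the placebo column to the E6011 column is 17.9/22.0 = 0.81 for a responder and 8.2/12.8 = 0.64 for a rescue failure.

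**Step 3: can the E6011-phase count be found by subtracting tables?** The tables count patients, so someone with the same term before and after the switch is counted once in the entire-administration table. For patients who go straight to the extension, the E6011-phase count lies between (entire − induction) and entire. As an example, suppose 3 of 12 have a term in induction and 5 of 12 in the entire period. The count is then between 5 − 3 = 2 and 5, or 17% to 42%. The rescue table adds what happened in rescue but leaves the same gap for the extension.

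**The case against.** Several counter-arguments have force.

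- **The blinded comparison is clean.** Events are assigned by period of onset, so the induction tables hold only double-blind events. This stands.
- **The rescue table is not a mixture.** It holds only events starting on open-label E6011, and adding its two columns gives the all-E6011 rescue count. This stands; only the column heading misleads there.
- **Long-term safety is not left unaddressed.** The E6011 column is E6011 experience from Week 0. Laboratory, vital-sign and CD4 data are summarised by visit or time point. Dated listings on about a dozen patients could be read individually. This stands, but a reconstruction from listings is not a pre-specified summary of a stated objective.
- **Columns by randomised sequence are a recognised choice in a descriptive study.** This is fair, provided the headings say so and an E6011-phase count is also given. The plan provides neither.

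Three stronger readings are tempting, and the documents do not support them.

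- **An undeclared departure from the protocol.** Protocol 9.7.1.8 says safety summaries "are to be calculated by treatment group based on the actual treatment received", while SAP 6.11 states "There are no modifications from the statistical section in the protocol". But Protocol 9.7.1 says that the text up to 9.7.1.9 mainly concerns induction, where the phrase naturally means as treated rather than as randomised. SAP 5.2 implements that. Protocol 9.7.1.10 asks for the same analyses over the whole dosing period, and 9.7.1.11 itself keeps treatment-group columns in follow-up. No clear conflict is shown.
- **An error in the exposure definition.** SAP 4.4 counts from "date and time of first double-blind IMP administration + 14 days", so placebo and E6011 time are added together. But the quantity is exposure to study product, which by Protocol 9.5.1.5.1 includes placebo. It measures what it names; E6011 patient-years would be an addition.
- **An E6011 effect always looking almost as common under placebo.** Step 2 shows that this depends on the path, and the documents give no mix of paths.

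**Conclusion.** The concern holds as a gap in the adverse event tables after Week 12. In the entire-administration and study-wide tables, E6011-phase events in placebo-randomised patients are pooled with their placebo events under a placebo heading. No table counts events from the first E6011 dose across all exposed patients. For patients who enter the extension, subtraction between tables does not supply that count.

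The shares of 62.5%, 79% and 83% assume scheduled dosing and visits; early discontinuation would change them. The convergence figures also assume no placebo risk and one constant risk under two-weekly dosing, four-weekly dosing and the 70 days off drug. They show direction and are not a forecast.

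Severity is minor. The double-blind comparison is untouched, the analysis is descriptive, no decision rule uses these tables, and the data needed to repair them are already collected. It is a cheap improvement.

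**What to change.** Before the entire-administration database is locked (Protocol 9.7 fixes the analysis plan before each lock):

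1. Add to SAP 6.1 an analysis period called 'E6011 phase', running from the first E6011 dose (Week 0, or the first open-label dose for placebo-randomised patients) to 70 days after the last E6011 dose.
2. Repeat tables c to k of SAP 6.9.1 for this period in one 'All E6011' column, with patient-years counted from the first E6011 dose. There is no concurrent control, so the column is read descriptively.
3. Head the rescue and entire-administration columns 'Placebo then E6011' and 'E6011 then E6011'.
4. Leave the induction tables as planned.

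The cost is SAP text, programming and a set of extra tables. Dose dates and event start dates are already recorded, so no visit, sample or data item is added.

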6.2 Missing Data Handling

6.2.1 Handling of adverse event missing/partial dates

Imputation of adverse events dates will be performed only for classification purposes.

If an adverse event date is incomplete, an imputation algorithm will be used to classify the adverse event as pre-treatment, treatment-emergent, or post-treatment and any derivation that includes dates (e.g., period determination).

The algorithm for imputing start date will be conservative and will cover the following scenarios:

- If only day is missing, the day will be set to the first day of the month
- If the month and day are missing, the day and the month will be set to 1 Jan
- If the year, month and day are missing, no imputation will be performed

If the date does not indicate that the adverse event started prior to treatment or after the treatment-emergent adverse event period, the adverse event will be classified as treatment-emergent.

The algorithm for imputing end date will be conservative and will cover the following scenarios:

- If only day is missing, the day will be set to the last day of the month
- If the month and day are missing, the day and the month will be set to 31 Dec
- If the year, month and day are missing, no imputation will be performed

These data imputations are for categorization purpose only and will not be used in listings.

When the date and time of the first IMP administration is missing, all adverse events that occurred on or after the day of randomization should be considered as treatment-emergent adverse events.

If the assessment of the relationship to IMP is missing, then the relationship to IMP has to be assumed and the adverse event considered as such in the frequency tables of possibly related adverse events. These data imputations are for categorization purpose only and will not be used in listings.

If the severity is missing for 1 of the treatment-emergent occurrences of an adverse event, the maximal severity on the remaining occurrences will be considered. If the severity is missing for all the occurrences the maximal severity will be imputed to "Severe". These data imputations are for categorization purpose only and will not be used in listings.

6.2.2 Handling of any partial date required to calculate corresponding durations

For Crohn disease duration, partial dates will be imputed. If only the day is missing, the day will be replaced by the half-month-day. If the month is missing, the month will be replaced by June. No imputation of years will be done.

6.2.3 Handling of medication missing/partial dates

Imputation of medications dates will be performed only for classification purposes.

If a medication date is incomplete, an imputation algorithm will be used to classify the medication as prior or concomitant.

The algorithm for imputing start date will be conservative and will cover the following scenarios:

- If only day is missing, the day will be set to the first day of the month
- If the month and day are missing, the day and the month will be set to 1 Jan
- If the year, month and day are missing, no imputation will be performed

The algorithm for imputing end date will be conservative and will cover the following scenarios:

- If only day is missing, the day will be set to the last day of the month
- If the month and day are missing, the day and the month will be set to 31 Dec
- If the year, month and day are missing, no imputation will be performed

These data imputations are for categorization purpose only and will not be used in listings.

6.3 Patient Disposition

This section describes patient disposition for both patient study status and the patient analysis populations.

Screened patients are defined as all patients who originally signed the informed consent.

Randomized patients consist of all screened patients with a treatment group allocated and recorded in the IRT database, regardless of whether the treatment kit was used or not.

For the patient study status, the total number of patients in each of the following categories will be presented in the clinical study report using a flowchart diagram or summary table:

- Screened patients
- Screen failure patients and reason for screen failure
- Randomized patients
- Randomized but not treated patients
- Randomized and treated patients
- Patients who discontinued study treatment by main reason for permanent treatment discontinuation

- Status at last study contact: Information collected will be compiled from the patient status panel and information of lost-to-follow-up status from the end of study (EOS) module of the eCRF which was defined as below.

Reason for study discontinuation will be described:

- Progression of the primary disease
- An adverse event unrelated to progression of the primary disease
- An inclusion criterion has turned out to be not met
- An exclusion criterion has turned out to be met
- The patient used prohibited drug(s) or drug(s) with restricted use
- The subject's pregnancy has been confirmed
- Insufficient therapeutic effect (including less than 70 points decrease in CDAI after Rescue Phase)
- The subject requires a surgical operation
- Withdrawal of consent by the subject
- Lost to follow-up
- Discontinuation of the entire Study by the Sponsor
- Other reason by which the Study Treatment is not appropriate as judged by the Sponsor/Investigator

For all categories of patients (except for the screened and non-randomized categories), percentages will be calculated using the number of randomized patients as the denominator. Reasons for treatment discontinuation will be supplied in tables giving numbers and percentages by treatment group. This summary will be provided by treatment group.

All critical or major deviations potentially impacting efficacy analyses, randomization, and drug dispensing irregularities, and other major or critical deviations will be summarized in tables giving numbers and percentages of patients with deviations by treatment group. The deviations will be defined and listed in the Protocol Deviation Document.

Additionally, the analysis populations for safety, efficacy will be summarized in a table by number of patients on the randomized population:

- Efficacy populations: FAS population, PPS population
- Safety population

6.3.1 Randomization and drug dispensing irregularities

Randomization and drug-dispensing irregularities occur whenever:

- A randomization is not in accordance with the protocol-defined randomization method, such as
 - a) an ineligible patient is randomized, b) a patient is randomized twice

OR

- A patient is dispensed an IMP kit not allocated by the protocol-defined randomization, such as a) a patient at any time in the study is dispensed a different treatment kit than as randomized (which may or may not contain the correct-as-randomized IMP), or b) a non-randomized patient is treated with IMP reserved for randomized patients.
- Randomization and drug-dispensing irregularities will be monitored throughout the study and reviewed on an ongoing basis.

All randomization and drug-dispensing irregularities will be documented in the clinical study report. If the number of irregularities is large enough to make a tabular summary useful, the irregularities will be categorized and summarized among randomized patients (number and percentages)

Randomization and drug-dispensing irregularities to be prospectively identified include but are not limited to:

**Randomization and drug allocation
irregularities**

- Kit dispensation without IRT transaction
- Erroneous kit dispensation
- Kit not available
- Randomization by error
- Patient randomized twice
- Patient switched to another site

